### 5.2.3. Sample Size

This randomized, controlled PMCF study will enroll a total of 34 patients, allocated 1:1 to:

- **Test group (n = 17):** CAF + SCTG with adjunctive hyaDENT BG®
- **Control group (n = 17):** CAF + SCTG without hyaDENT BG®

The slight increase from the initially planned 30 patients is intended to accommodate an approximate 10% drop-out rate, ensuring that about 30 patients (15 per group) complete the study as evaluable. The sample size calculation remains based on the primary endpoint (CRC at 12 months) with 30 evaluable patients, while the additional 4 subjects provide a margin of safety for potential losses to follow-up.

The sample size was determined to reliably detect a clinically meaningful difference in the primary outcome. Previous randomized studies (e.g. Pilloni et al. 2019) have reported CRC rates of roughly 80% with CAF+HA versus 33% with CAF alone, an absolute difference of ~47 percentage points. Using this large effect size (47 pp), a two-sided  $\alpha = 0.05$ , and power ( $1-\beta$ ) of 80%, a minimum of 15 patients per group was deemed sufficient to demonstrate a statistically significant difference in CRC. By enrolling 17 per group (34 total), the study preserves this power assumption while accounting for possible drop-outs, thereby maintaining at least 15 analyzable subjects in each arm.

**Sensitivity Analysis of Power:** The sample size is powered to detect a large CRC difference (47 pp), based on prior data. However, if the true effect is smaller (e.g. 20–30 pp), the study may be underpowered to reach statistical significance. This highlights a potential risk of type II error for modest but clinically relevant differences. Exact power estimates for these scenarios will be calculated by the statistician using final parameters. Overall, the sample size represents a practical balance between feasibility and detecting a meaningful effect

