## 1. INTRODUCTION AND RATIONALE

### 1.1. Introduction

Gingival recession (GR) is a frequent mucogingival deformity characterized by the apical displacement of the gingival margin with exposure of the root surface beyond the cemento-enamel junction (CEJ) [1–3]. Its prevalence increases with age and may lead to dentin hypersensitivity, root caries, plaque retention, aesthetic impairment, and patient discomfort [4,5]. Among the available treatment modalities, the coronally advanced flap (CAF), particularly when combined with a subepithelial connective tissue graft (SCTG), is a **well-documented and widely adopted approach** for the management of single and multiple recession-type defects, providing predictable root coverage, gain of keratinized tissue, and long-term stability [6–8]. However, CAF + SCTG procedures may still be associated with postoperative morbidity, donor-site discomfort, and incomplete root coverage in some cases [9,10]. Therefore, adjunctive strategies aimed at enhancing wound healing and increasing the probability of complete root coverage (CRC) remain of significant clinical interest.

Hyaluronic acid (HA), a high-molecular-weight, non-sulfated glycosaminoglycan, is a key component of the periodontal extracellular matrix and plays a pivotal role in angiogenesis, cell migration, proliferation, and differentiation during tissue healing [11–13]. HA has been shown to accelerate granulation tissue formation, modulate inflammatory responses, and stimulate fibroblast and keratinocyte activity [14–16]. Preclinical studies demonstrated that HA enhances vascularization, supports osteoinduction, and upregulates osteogenic markers such as Runx2, alkaline phosphatase (ALP), and osteocalcin [17,18]. In vitro studies further confirm that HA promotes fibroblast proliferation, migration, and extracellular matrix synthesis [19,20], while cross-linked formulations prolong its bioactivity in surgical wounds [21]. Moreover, HA exhibits bacteriostatic properties against periodontopathogens such as *Aggregatibacter actinomycetemcomitans* and *Porphyromonas gingivalis* [22], potentially reducing early contamination of surgical sites.

The adjunctive use of HA in periodontal regenerative and mucogingival surgery has been investigated in several clinical studies. Randomized controlled trials (RCTs) demonstrated significantly greater clinical attachment level (CAL) gain, mean root coverage (MRC), and CRC when

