### 5.5. Discussion of Study Design

This investigation is designed as a post-market clinical follow-up (PMCF) study, since both the test and control interventions (CAF + SCTG with or without adjunctive hyaDENT BG®) are established techniques in periodontal plastic surgery. A prospective, randomized, controlled parallel-arm design was chosen to generate high-level clinical evidence on the adjunctive use of cross-linked hyaluronic acid versus the conventional gold-standard alone. To minimize bias and account for baseline variability, the randomization will be *stratified by recession type* (Cairo RT1 vs RT2 classification), ensuring that defects of differing initial severity are evenly distributed between the test and control groups. Allocation concealment is maintained via sealed, sequentially numbered opaque envelopes, and blinding is upheld for outcome examiners, which together strengthen the internal validity of the trial.

The sample size and power considerations have been tailored to balance scientific rigor with practical feasibility. The trial plans to recruit 34 patients to allow for a ~10% drop-out rate, aiming for 30 patients to complete the 12-month follow-up. This enrollment strategy preserves the statistical power of the study by compensating for potential attrition. The sample size is driven by the primary outcome (complete root coverage at 12 months), which is a critical clinical and esthetic benchmark in mucogingival surgery. Detecting a significant difference in the proportion of sites with complete root coverage between groups will directly address the primary objective and could validate the added value of hyaluronic acid in enhancing surgical outcomes.

In addition to the primary endpoint, the study will evaluate multiple secondary endpoints covering clinical efficacy (such as mean root coverage, CAL gain, and keratinized tissue gain), patient-centered outcomes (pain/discomfort levels and oral health-related quality of life), and esthetic results (RES score). A hierarchical statistical testing plan has been incorporated for these secondary endpoints to allow a confirmatory interpretation of the most relevant

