## **7. CLINICAL TRIAL**

### **7.1. Sample Size and Randomization**

Each patient will be randomly assigned to one of the two study groups (test or control) in a 1:1 ratio. The randomization sequence will be generated using a computer program (e.g., IBM SPSS) with stratification by recession type (Cairo classification RT1 vs RT2) and using permuted

blocks of random sizes. This stratified, blocked randomization ensures that patients with RT1 and RT2 recession defects are equally balanced across the two groups, preventing any imbalance in baseline recession severity. Allocation concealment will be maintained through the use of opaque, sealed, sequentially numbered envelopes. An independent investigator (not involved in the treatment) will open the next envelope in sequence immediately after flap elevation, thereby revealing the group assignment. The treating surgeon will thus be unblinded at the point of graft placement (since they must know whether to apply the HA gel), but the patients will not be explicitly informed of their group allocation. (Patients might potentially guess their group based on postoperative symptoms or the presence of the HA application, so complete patient blinding cannot be guaranteed; however, all outcome assessors remain fully blinded to group assignment.)

Based on the sample size calculations and previous study data, approximately 17 patients per group (34 total) will be enrolled in this trial. This enrollment target includes a buffer for potential drop-outs, with the goal of ending up with at least 15 evaluable patients in each arm at study completion. The groups are defined as follows:

- **Test group (n ≈ 17):** CAF + SCTG with adjunctive hyaDENT BG® (HA applied at the recipient site).
- **Control group (n ≈ 17):** CAF + SCTG without the adjunctive hyaDENT BG® (no HA application).

By employing stratified randomization and concealing the allocation, the study design mitigates selection bias and ensures that both groups are comparable with respect to key prognostic factors (notably the recession type). The 1:1 allocation with an effective sample of ~30 completers (15 per group) provides sufficient power to detect the expected difference in the primary endpoint, while the slight over-enrollment to 34 accounts for attrition and preserves statistical integrity.

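### The sample size borrows its control rate and 47-point effect from an ungrafted-flap comparison, so the stated power is not supported for CAF+SCTG with versus without HA

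*Protocol*

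**What the plan says.** Section 5.2.3 takes its planning rates from an earlier randomised trial: "CRC rates of roughly 80% with CAF+HA versus 33% with CAF alone, an absolute difference of ~47 percentage points". With a two-sided alpha of 0.05 and 80% power, it concludes that "a minimum of 15 patients per group was deemed sufficient to demonstrate a statistically significant difference in CRC". Enrolment is 17 per group, to keep 15 evaluable after about 10% drop-out.

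The same section defines this trial's control as "CAF + SCTG without hyaDENT BG", and the test arm as the same operation with the gel added. Section 7.4 confirms that both groups receive the graft.

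The protocol describes the grafted procedure favourably. Section 1.1 speaks of CAF, particularly with the graft, as "providing predictable root coverage, gain of keratinized tissue, and long-term stability", and section 5.5 describes the comparison as HA "versus the conventional gold-standard alone". No section gives a CRC rate for it.

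A sensitivity paragraph in 5.2.3 accepts that a true effect of 20 to 30 points may leave the study underpowered. It gives no figures, leaves them to a later calculation, and does not mention that the comparator differs. Section 7.1 nevertheless says that 15 completers per group "provides sufficient power to detect the expected difference in the primary endpoint".

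**The concern.** The 33% is a rate for a procedure that no patient in this trial undergoes, and the 47 points measure what HA adds to a flap without a graft. The primary hypothesis in 4.4.1 asks what HA adds to a flap with a graft. Both numbers could differ in that setting: the control rate may be higher, which leaves less room for improvement, and the increment may be smaller. The populations differ too. By its title in the bibliography, the cited trial covers Miller class I single recessions, whereas section 5.2.1 admits RT1 and RT2.

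This calculation is the only justification for the sample size on the primary endpoint. A reader of the results will set a non-significant finding against a stated 80% power, and that figure belongs to a different comparison.

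**Working it through.** **Inputs from 5.2.3:** test rate 0.80, control rate 0.33, difference 0.47, two-sided alpha 0.05, power 0.80, 1:1 allocation, 15 evaluable per arm. The protocol gives no CAF+SCTG CRC rate, so every control rate other than 33% below is an assumption, shown as a range.

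**Step 1: the plan's own figure.**
- Unpooled normal formula: n = (1.96 + 0.8416)² × (0.80×0.20 + 0.33×0.67) / 0.47² = 7.849 × 0.3811 / 0.2209 = 13.5, so 14 per arm.
- Pooled formula, mean rate 0.565: n = [1.96 × √(2×0.565×0.435) + 0.8416 × √0.3811]² / 0.2209 = (1.374 + 0.520)² / 0.2209 = 16.2, so 17 per arm.

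The stated 15 lies between the two. The arithmetic is roughly reproduced; the difficulty is in the inputs.

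**Step 2: the ceiling.** The largest possible gain is 1 minus the control rate. A 47-point gain needs a control rate of at most 1.00 − 0.47 = 0.53. At 60% control the most that can be gained is 40 points; at 70% it is 30.

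**Step 3: exact power at 15 per arm.** Both binomial distributions are enumerated in full, and the probabilities of all outcomes with two-sided p ≤ 0.05 are summed. Two tests are shown because the protocol does not say which one the calculation used.

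| Control | Test | Gain (points) | Fisher | Chi-square, uncorrected |
|---|---|---|---|---|
| 33% | 80% (protocol's rates) | 47 | 61% | 76% |
| 33% | 63% | 30 | 23% | 37% |
| 33% | 53% | 20 | 10% | 19% |
| 50% | 80% | 30 | 25% | 42% |
| 60% | 80% | 20 | 11% | 23% |
| 60% | 90% | 30 | 33% | 51% |
| 70% | 90% | 20 | 15% | 28% |
| 50% | 97% | 47 | 82% | 92% |
| 60% | 100% | 40 | 78% | 91% |
| 70% | 100% | 30 | 48% | 70% |

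**Step 4: reading the table.** The first row is the baseline. Part of any shortfall in the Fisher column comes from that test at this sample size and not from the comparator. Comparing 33% versus 80% with 50% versus 97% shows that a higher control rate does not by itself lower power when the 47 points are kept. Power falls when the increment shrinks. At control rates of 50% to 60%, power near 80% requires almost complete success in the test arm. At 70%, even 100% in the test arm does not reach it.

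**The case against.** Four points can be made for the plan.

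1. A reader might infer that the 47-point effect does not apply here, or that the stated power does not exist. The documents do not go that far. They give no CRC rate for CAF+SCTG and no estimate of what HA adds to a graft, so they show neither a control rate above 53% nor an increment below 47 points. Favourable cases such as 50% versus 97% keep the power. This objection stands: the borrowed figures are unsupported for this comparison, not disproved.

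2. The favourable description of the grafted procedure is not evidence of a high CRC rate. Predictable coverage is not complete coverage, and section 1.1 also says that coverage can remain incomplete in some cases. Admitting RT2 defects leaves the control rate more open still. This stands too, and it is why the control rates above are only assumptions.

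3. The sensitivity paragraph already concedes low power at 20 to 30 points and names the type II error risk. It softens the problem but does not resolve it: it has no figures, does not mention the different comparator, and keeps 47 points as the base case.

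4. A reader might also infer that a null result will be reported as showing that HA adds nothing. Nothing in the protocol says so. Rules for confidence intervals and for interpreting non-significance may properly sit in the statistical analysis plan.

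**Conclusion.** The point holds as a lack of support. The planning rates come from CAF+HA versus CAF alone, the trial compares CAF+SCTG with and without HA, and nothing in the protocol connects the two. The 80% power in 5.2.3 and the sufficiency claim in 7.1 are therefore not established for this trial.

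The size of the problem depends on two numbers that the protocol does not give: the CAF+SCTG control rate and the HA increment. For assumed control rates of 50% to 70% and test rates of 80% to 90%, the four pairs tabulated have power of 11% to 33% by Fisher and 23% to 51% by chi-square. Power near 80% returns only if HA brings CRC close to 100% from a control rate of about 50% to 60%. The 53% ceiling is exact arithmetic, but whether it is exceeded is unknown. The stated 15 per arm is not itself a calculation error.

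**What to change.** In 5.2.3:
- Say that the cited rates are for a flap without a graft.
- State an assumed CRC rate for CAF+SCTG in RT1/RT2 defects with its source, and the increment expected from HA on top of it.
- Replace the sentence that defers the power estimates with a table at 15 per arm over a range of control rates. Include the 33% versus 80% line and name the test used.

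In 7.1, remove or qualify the statement that the sample "provides sufficient power to detect the expected difference in the primary endpoint". In 5.5, qualify to match the remarks that the enrolment plan preserves power and that the sample is adequate.

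The cost is protocol wording and one short table. Enrolment, arms, endpoint and analysis stay as they are. The power on record will look less favourable unless a sourced control rate and increment support it.

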##### **5.2.4.1. Procedures for Replacement of Patients**

Patients who withdraw from the study after randomization will not be re-enrolled. Their data will be included in the analysis following the intention-to-treat (ITT) principle whenever possible.

If a patient withdraws during the enrolment phase and prior to surgery, the investigator will make all reasonable efforts to recruit a new eligible patient in order to maintain the planned sample size (30 patients, 15 per group). This approach is intended to preserve the statistical power of the study and the validity of the comparative analysis between the test and control groups.

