## **6. MATERIALS AND METHODS**

### **6.1. Study outline**

A prospective, experimental, controlled, randomized study will be performed on 30 patients divided into two groups. In the test group, patients will undergo coronally advanced flap surgery combined with connective tissue graft with application of hyaluronic acid. In the control group, patients will undergo the same surgery without the application of hyaluronic acid.

The study will be complemented by an in vitro component in which a sample of the connective tissue graft will be taken from each patient to isolate fibroblast cells, culture them, and evaluate their viability, proliferation, differentiation, and mediation in cell signaling in the presence or absence of hyaluronic acid.

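### With 15 evaluable patients per group, exact power for CRC 80% vs 33% is below the stated 80% (76% chi-square, 61% Fisher); two sections also still give 30 as the planned size instead of 34

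*Protocol*

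**What the plan says.** Protocol section 5.2.3 takes from earlier randomised work "CRC rates of roughly 80% with CAF+HA versus 33% with CAF alone", that is, "an absolute difference of ~47 percentage points". With two-sided alpha 0.05 and 80% power it concludes that "a minimum of 15 patients per group was deemed sufficient to demonstrate a statistically significant difference in CRC". It then enrols 17 per group (34 in total) to cover about 10% drop-out, "thereby maintaining at least 15 analyzable subjects in each arm". Possible underpowering is acknowledged only for smaller true differences of 20 to 30 points. Section 7.1 repeats that about 30 completers, 15 per group, give enough power for the expected difference. Neither section names the sample-size formula or the test for the primary endpoint.

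On the number of patients, sections 5.2.3, 5.5 and 7.1 say 34 enrolled with about 30 completing. Section 5.2.4.1 says that patients lost before surgery are to be replaced "to maintain the planned sample size (30 patients, 15 per group"), and section 6.1 says the study "will be performed on 30 patients divided into two groups".

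**The concern.** The 80% power is the main quantitative property claimed for the design, and it is claimed at the most favourable effect the protocol considers. At 15 per group the usual formulas and tests for two proportions disagree noticeably, so it matters which of them produced the figure. If the test eventually used has less than 80% power at 47 points, a reader of a non-significant result would give it more weight against the hypothesis than the design justifies, because the protocol warns of low power only for smaller effects.

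Two lesser matters bear on the same claim. A drop-out allowance gives an expected number of completers and cannot secure a minimum in each arm. And the replacement rule, which is justified in 5.2.4.1 by preserving power, refers to a planned size that 5.2.3 has replaced.

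**Working it through.** **Inputs, all from section 5.2.3.** p1 = 0.80, p2 = 0.33, d = 0.47, two-sided alpha 0.05 (z = 1.96), power 80% (z = 0.8416), 1:1 allocation, 15 evaluable and 17 enrolled per group, drop-out about 10%. The test is not given, so several are shown.

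**Step 1: reproducing 15 per group.**

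- Unpooled normal approximation: n = (1.96 + 0.8416)² × (0.80×0.20 + 0.33×0.67) / 0.47² = 7.849 × 0.3811 / 0.2209 = 13.5, so 14 per group. Its approximate power at 15 is Φ(0.47/√(0.3811/15) − 1.96) = Φ(0.989) = 83.9%. On this formula 15 is enough.
- Pooled normal approximation, mean rate 0.565: n = [1.96√(2×0.565×0.435) + 0.8416√0.3811]² / 0.2209 = (1.374 + 0.520)² / 0.2209 = 16.2, so 17 per group. Approximate power at 15 is 76.5%.
- Arcsine approximation: n = 16.0 per group; power at 15 is 77.4%.
- Pooled with continuity correction: n = 20.3, so 21 per group.

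**Step 2: exact power.** For each pair of outcomes (i successes of n under 0.80, j of n under 0.33), add up the product of the two binomial probabilities wherever the test rejects at two-sided 0.05.

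| Test | 15 per group | 17 per group |
|---|---|---|
| Fisher exact | 61.1% | 72.9% |
| Chi-square with Yates correction | 61.0% | 72.9% |
| Barnard / Boschloo | 75.0% | not computed |
| Chi-square, uncorrected | 76.3% | 83.7% |
| Z, unpooled variance | 79.3% | 84.1% |

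Reading 33% as one third lowers the 15-per-group figures slightly (Fisher 60.3%, chi-square 75.7%, unpooled Z 78.8%). The smallest size with 80% exact power is 16 per group for chi-square (80.5%). For Fisher it is 19 (80.0%), with a dip to 79.5% at 20 and 80.9% at 21.

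**Step 3: type I error at 15 per group.** The same enumeration with a common rate in both groups, for rates 0.30, 0.50 and 0.565, gives:

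- unpooled Z: 6.7%, 5.7% and 6.0%;
- uncorrected chi-square: 5.5%, 4.6% and 4.7%;
- Fisher: about 1.7%, 1.7% and 1.6%.

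The test closest to 80% power exceeds the stated alpha at each of these rates, and Fisher is well below it.

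**Step 4: drop-out.** 30 / (1 − 0.10) = 33.3, so 34 is the right inflation of 30. Expected completers are 17 × 0.90 = 15.3 per arm. If each patient drops out independently with probability 0.10 (an assumption; the protocol gives only the rate), an arm keeps at least 15 when it loses at most 2 of 17, probability 0.762. Both arms do so with probability 0.762² = 0.58.

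**Step 5: planned size.** 34 enrolled in 5.2.3, 5.5 and 7.1; 30 (15 per group) as planned size in 5.2.4.1; 30 patients in 6.1. Section 5.2.3 describes 30 as the number planned initially and explains the increase, so the other two figures read as text that was not updated.

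**The case against.** The strongest reply is that 15 is not a miscalculation. A textbook formula gives 14 per group, and 15 satisfies it with approximate power near 84%. That stands: a reader might infer a plain arithmetic slip, and the document does not support that. What the reply does not rescue is the power claim itself. The approximation is optimistic at this size, since the matching Z test has exact power of 79.3%, and it comes that close only by exceeding the 0.05 level.

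Second, the choice of test may properly be left to the SAP, which is not shown. This also stands, and the absence of a named test is not in itself the fault. A reader might infer that the trial has only 61% power, but that follows only if Fisher's test is used, and Fisher is conservative here. With tests nearer the nominal level the gap is 4 to 5 points. Still, none of the tests checked reaches 80% at 15 per group.

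Third, withdrawn patients are to be analysed by intention to treat where possible, and 12-month CRC is to be collected before final withdrawal where possible. With all 17 per group contributing, chi-square power is 84%. This is a fair mitigation, but sections 5.2.3 and 7.1 attach the power claim to 30 evaluable patients.

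Fourth, nearby wording is softer than the promise of at least 15: 5.2.3 also says about 30, 5.5 describes an aim, and 7.1 a goal. That makes this a small correction.

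Finally, a reader might infer from 5.2.4.1 and 6.1 that recruitment would stop at 30, leaving 30 × 0.90 = 27 evaluable. The documents do not support this: 5.2.3 explains the rise to 34, 5.5 and 7.1 repeat it, 5.2.4.1 concerns replacement and is no stopping rule, and its 15 per group equals the evaluable target.

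**Conclusion.** The statement that 15 evaluable patients per group give 80% power at 80% vs 33% is not borne out by any test checked. The shortfall is about 1 point with an unpooled Z test that exceeds its nominal level, 4 with the uncorrected chi-square, 5 with Barnard or Boschloo, and 19 with Fisher. At 17 per group with no losses, chi-square exceeds 80% and Fisher does not. These figures take the protocol's two CRC rates as given; whether those rates suit this comparison is a separate question. The promise of at least 15 per arm is unsupported; the 58% depends on the assumed independent drop-out. The 30 in sections 5.2.4.1 and 6.1 contradicts the 34 elsewhere and needs aligning, though it does not show that fewer patients will be recruited. Nothing here establishes that the trial must be enlarged.

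**What to change.** - In section 5.2.3, and where 7.1 says that 15 per group provides enough power, state the formula and the test behind 15, and give the exact power for that test at 15 and at 17 per group. For the uncorrected chi-square this reads 76% and 84%; for Fisher's exact test, 61% and 73%. Section 5.5 quotes no power percentage and needs no change on this count.
- In 5.2.3, replace "thereby maintaining at least 15 analyzable subjects in each arm" with wording to the effect that about 15 evaluable patients per arm are expected.
- In 5.2.4.1 and 6.1, replace 30 patients (15 per group) with 34 enrolled (17 per group), as in 5.2.3, 5.5 and 7.1.

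These are wording changes only. No additional enrolment is needed, and the one cost is that the stated power becomes less favourable.
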